15.5. Interim analyses

Data will be processed and analysed upon completion of the 6- and 12-month follow-up periods, respectively. However, no formal interim analyses are planned to support decisions regarding modification

or early termination of the trial in accordance with the proposed study timeline. The trial management team will periodically monitor recruitment progress, data quality, and participant safety. Any serious adverse events will be reported in accordance with applicable ethical and regulatory requirements, as outlined in the study protocol.

15.6. Descriptive Analyses

Descriptive statistics will be employed to summarise baseline sociodemographic characteristics, clinician-related variables, and psychometric measures across both intervention and control groups. Categorical variables will be presented as absolute frequencies and corresponding percentages. For continuous variables, means and standard deviations (SD) will be reported when distributions are symmetrical; otherwise, medians and interquartile ranges (IQR) will be used. Discrete numerical variables will also be summarised using medians and IQRs.

Missing data will be documented in detail. The number and proportion of missing values for each variable will be reported by study arm.

15.7. Primary Objective

The primary outcome data (MANSA scores) will be summarised at baseline and 6 months. At each time point, the number of observations, means, and standard deviations will be reported separately for the intervention and control groups to support interpretation of changes over time.

A mixed-effects linear regression model will be used to evaluate the effect of the intervention on MANSA scores at 6 months. Fixed effects will include treatment group (intervention vs control) and the baseline MANSA score to adjust for initial differences. Clinician or healthcare practitioners clusters will be modelled as a random effect to account for intra-cluster correlation.

The model will estimate the adjusted mean difference in MANSA scores between the two groups, with corresponding 95% confidence intervals (CIs) and p-values.

Formally, the model can be expressed as:

$$y = X\beta + Z\gamma + \varepsilon$$

y is the vector of observed MANSA scores, X is the design matrix for fixed effects, β is the vector of fixed-effect parameters (including the treatment group and baseline MANSA), $Z\gamma$ represents the random effects, with Z being the design matrix for random effects and γ the corresponding random-effect parameters (clinician clusters) and ε is the vector of residual errors.

In lay terms:

Mixed-effects model = Fixed effects (treatment arm + covariates) + Random effects (clinician clusters). The mixed-effects model accounts for both fixed effects—such as treatment group and relevant covariates—and random effects arising from the clustering of participants within clinicians.

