12.7. Randomisation

The unit of randomisation will be the individual participant. Site-stratified blocked randomisation, with a variable block size ranging from two to four, will be performed on a rolling basis during the recruitment period. A randomisation schedule will be defined for each health centre (study site). Within each stratum, participants will be randomised in a 1:1 ratio to either DD+ or the control group. Randomisation will be performed using REDCap or via a phone call, following the corresponding randomisation schedule.

Figure 3. Study Randomisation Summary

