15.2. Sample Size Determination

The sample size calculation for this study will be based on parameters derived from previous DIALOG+ trials (35). A standard deviation of 0.9 for the MANSA and a correlation of 0.4 between baseline and follow-up measurements will be assumed, while an effect size of 0.4 points on the MANSA will be considered the minimal clinically important difference (MCID) for quality of life in this patient population. Based on these parameters, a total of 90 participants per group will be required to achieve 90% power at the 5% two-sided significance level. To account for an anticipated 20% attrition rate, the final sample size will be set at 226 participants (113 per group).

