16. STUDY LIMITATIONS AND BIAS CONTROL

Due to the diversity of settings in terms of geographic location and sociodemographic characteristics, the risk of bias due to lack of representativeness of the Colombian population will be low. The randomisation procedure is also expected to generate balanced groups, reducing the risk of differential selection bias and minimising the chances of differential losses. However, since participants in the control group will have less contact with the study team and will be aware of their allocation due to unblinding, there is a risk of higher losses in this group. To mitigate this, routine phone calls will be made to control participants as reminders for the 6- and 12-month follow-up assessments.

A risk of contamination bias exists due to the public availability of the DIALOG+ application in the Play Store. However, for the active group, the intervention will be delivered by a trial clinician in the intervention appointments. In contrast, the follow-up visits for the control group will be through brief phone calls. Neither the trial clinician nor the researcher in charge of the follow-up call will be part of the patient care team. Furthermore, the fact that the application is publicly available will not be explicitly disclosed to participants to minimise the risk of bias.

The lack of blinding may also introduce bias through QoL outcome overestimation. However, outcome assessors and statisticians will remain blinded to allocation to reduce the risk of overestimating the effect or its magnitude. The risk of allocation concealment failure exists, but it is limited because the allocation will be automatically provided by the REDCap platform and only disclosed at the end of the baseline assessment visit.

A risk of outcome misclassification also exists. Although the diagnostic scales and tests used are validated and widely applied, the absence of measurement errors cannot be guaranteed. However, any misclassification is not expected to be differential. Finally, the risk of confounding is low due to randomisation, but not negligible. Therefore, statistical analyses for primary and secondary outcomes will adjust for relevant covariates, and the interpretation of results will consider the distribution of known variables among intervention and control groups.

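### Sections 15.7 and 16 do not fix the same primary model; one closed covariate list, with baseline PHQ-8 and GAD-7 added, would settle this at almost no cost

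*Protocol*

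**What the plan says.** Section 15.7 (Primary Objective) sets out a mixed-effects linear regression for MANSA at 6 months: "Fixed effects will include treatment group (intervention vs control) and the baseline MANSA score to adjust for initial differences". Clinician or practitioner clusters enter as a random effect. The formal definition beneath it names the same two fixed effects. A closing paragraph in lay terms then speaks more loosely of treatment arm plus covariates.

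Section 16 (Study Limitations and Bias Control) notes that some confounding risk remains after randomisation and concludes that "statistical analyses for primary and secondary outcomes will adjust for relevant covariates". No covariate is named there.

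Section 15.2 (Sample Size Determination) rests on baseline adjustment: "A standard deviation of 0.9 for the MANSA and a correlation of 0.4 between baseline and follow-up measurements will be assumed". It concludes that "a total of 90 participants per group will be required to achieve 90% power at the 5% two-sided significance level".

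Section 12.5 has PHQ-8, GAD-7 and AUDIT-C administered to all participants at or below the MANSA threshold, whether or not they already carry a mental health diagnosis. Section 12.10 places these scales at Visit 1. Randomisation closes Visit 2.

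**The concern.** Two statisticians could each follow this protocol and fit different primary models. One would use the two named fixed effects of 15.7. The other would add further covariates on the authority of Section 16. The primary analysis should allow only one reading.

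The open wording also hides a choice worth making deliberately. By design, baseline MANSA explains a modest share of the outcome variance. Depression and anxiety scores are plausible further predictors of later quality of life, and the trial already holds them for everyone it randomises. If they are prognostic, naming them would narrow the confidence interval for the treatment effect with no extra data collection. What is at stake is clarity of the primary model and a small amount of precision, not the validity of the comparison.

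**Working it through.** **Inputs from the protocol.** SD of MANSA 0.9, baseline to follow-up correlation 0.4, target difference 0.4 points, two-sided 5% level, 90% power and 20% attrition (all Section 15.2); 1:1 allocation (Section 12.7).

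**Step 1: reproduce the plan's figure.**
- Share of variance explained by baseline MANSA: 0.4² = 0.16.
- Residual SD: 0.9 × √(1 − 0.16) = 0.825.
- n per arm = 2 × (1.960 + 1.282)² × 0.825² / 0.4² ≈ 89.4, so 90.
- After attrition: 90 / 0.80 = 112.5, so 113 per arm and 226 in total.

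The stated sample size reproduces. Unadjusted follow-up scores would need 107 per arm and change scores 128, so the plan's figure is the one for baseline-adjusted analysis, consistent with 15.7.

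**Step 2: power of the model as named.** The standard error is 0.825 × √(2/90) = 0.123. Power = Φ(0.4/0.123 − 1.96) = Φ(1.293) = 90.2%.

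**Step 3: add baseline PHQ-8 and GAD-7.** The protocol gives no correlation between either scale and 6-month MANSA, so the further share of residual variance, p, is an assumption. The residual SD becomes 0.825 × √(1 − p). Keeping 90 completers per arm:

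| Assumed p | Residual SD | Power | Standard error relative to plan | Equivalent extra completers per arm |
|---|---|---|---|---|
| 0 (as named) | 0.825 | 90.2% | 1.00 | 0 |
| 3% | 0.812 | 91.0% | √0.97 = 0.985 | 90/0.97 − 90 ≈ 3 |
| 5% | 0.804 | 91.6% | √0.95 = 0.975 | 90/0.95 − 90 ≈ 5 |
| 10% | 0.783 | 92.9% | √0.90 = 0.949 | 90/0.90 − 90 = 10 |

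These figures use the normal approximation and, like Section 15.2, make no allowance for clinician clustering.

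**Step 4: cost in degrees of freedom.** Two more fixed effects use two degrees of freedom out of about 2 × 90 = 180.

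**Step 5: compare the wording.** The operative sentence and the formal definition in 15.7 agree on two fixed effects. Section 16 commits the same primary analysis to covariates it does not list. Section 15.9 adds further unspecified baseline covariates for the secondary outcomes, but the operative specification in 15.7 has no such clause. The conflict over the primary outcome therefore lies chiefly between 15.7 and Section 16.

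**The case against.** The strongest reply is that nothing here is wrong. With randomisation the treatment estimate is valid without PHQ-8 and GAD-7, and the design reaches its stated power on baseline MANSA alone. The gain from adding them rests on assumed values. A statistical analysis plan that is not shown may give the full list. The lay paragraph in 15.7 is most naturally a restatement, since baseline MANSA is itself a covariate. All of this stands, and it is why the point is an improvement and not an error. It does not remove the difference between a named model in 15.7 and an unnamed one in Section 16, which the protocol itself should resolve.

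Stronger readings are tempting and should be resisted.
- **Covariates chosen on observed balance or after seeing the data.** A reader might infer this from Section 16. But that section uses the distribution of known variables between arms to interpret results, not to select covariates. The only rule triggered by imbalance is in 15.11.7, and it covers the economic analysis.
- **Inflated type I error.** One might go on to claim this from a search over covariate sets. No section describes such a search, and the analyses are assigned to a blinded statistician.
- **The scales are ignored.** The documents show only that they are not named; the unnamed covariates of Section 16 could include them.

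The protocol also offers no specific support for adding age and sex to the primary model, so they are not proposed here. Whether study site, the stratification factor, belongs in the model is a separate question.

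**Conclusion.** The point holds as a reconciliation of wording together with a nearly free gain in precision. Sections 15.7 and 16 do not fix the same primary model, and two likely prognostic baseline scores that every randomised participant should have are not named in it.

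The estimate is unbiased either way, and the sample size of 226 stands. The gain is about 1 to 3 percentage points of power, from 90.2% to between 91.0% and 92.9%. It depends on the two scales explaining 3% to 10% of the variance left after baseline MANSA. That range is assumed. If they explained nothing further, the change would cost two degrees of freedom and gain nothing.

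**What to change.** - In 15.7, state one closed list for the primary model: treatment group, baseline MANSA, baseline PHQ-8 and baseline GAD-7 as fixed effects, with the clinician random effect. Bring the lay paragraph into line with it.
- In 15.4, include the same variables in the imputation model, so that it contains everything the analysis model uses.
- In Section 16, replace the open statement for the primary outcome with a reference to the list in 15.7.

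The cost is a protocol wording change and two degrees of freedom. No new data, visits or participants are needed. The change should be made before any outcome data are examined by arm.

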15.3. Analysis populations

The primary and Secondary (Effectiveness) analysis will follow the intention-to-treat (ITT) principle, including all randomised participants in the groups to which they were originally allocated, regardless of treatment received, adherence, or withdrawal. Participants who discontinue or deviate from the intervention will remain in their assigned group for analysis (49). Missing data will be imputed as specified in the following subsection.

15.4. Procedure for Accounting for Missing, Unused, and Spurious Data.

For the primary and secondary analysis of the outcome and in line with the intention-to-treat (ITT) principle, missing data will be addressed using multiple imputation by chained equations (MICE) (50). The imputation model will incorporate treatment group and relevant baseline covariates including study clinician age, sex, clinician, and baseline MANSA score or other measures that are relevant according to the objective of the analysis. The imputation will be conducted under the assumption that data are missing at random (MAR). Rubin's rules (51) will be applied to pool the estimates across multiple imputed datasets, thereby reflecting the uncertainty associated with the imputation process. This approach aims to preserve the structure of the data and reduce bias due to missingness.

A sensitivity analysis will be conducted to assess the impact of missing data assumptions, comparing multiple imputation estimates with those from a complete-case analysis.

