15.11.7. Analysis of cost-effectiveness

We will compute the ICER as the additional cost per additional QALY gained ($\Delta C/\Delta E$). Interpretation will use Colombia-relevant willingness-to-pay (WTP) benchmarks. Specifically, we will present cost-effectiveness acceptability curves (CEACs) across a WTP range and highlight the empirically estimated Colombia threshold of about US\$5,181 per QALY (\approx COP 17 million in 2019 prices) from Espinosa et al. (55) (IETS) updated to the study price year (2025) using DANE CPI. DIALOG+ will be described as cost-effective when the ICER lies below a WTP value deemed acceptable in Colombia, and we will report the probability of cost-effectiveness at the updated reference threshold and other policy-relevant WTP points.

Differences between trial arms in costs and outcomes will be estimated on an intention-to-treat basis, initially unadjusted and subsequently adjusted for pre-specified baseline covariates. If participant characteristics differ systematically between arms, adjusted models will include age, sex, NCD condition group (hypertension/obesity/T2DM), mental health condition group (anxiety, depression or alcohol misuse), baseline utility (EQ-5D-5L), baseline MANSA and WHOQOL-BREF, baseline total cost, and site (fixed effects).

Incremental costs will be estimated using mixed-effects generalized linear models appropriate for skewed data (primary: Gamma family with log link, or log-normal), including by random effect in the model for healthcare practitioners who delivered DIALOG+ considering clusters. Incremental cost-effectiveness will be estimated with linear mixed models including the same covariates.

Based on the results for quality of life, blood pressure control, glycated hemoglobin, and within-trial cost-effectiveness, we plan to conduct a modeled cost-effectiveness extension study over a 5-year time horizon from the healthcare perspective. In addition, a budget impact analysis with the same horizon will be carried out to support acceptability among decision-makers in the country.

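### The primary model's clinician random effect is undefined for control participants and site is not named, so the primary standard error depends on an unstated coding choice

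*Protocol*

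**What the plan says.** Section 15.7 gives the primary model explicitly. For the fixed part: "Fixed effects will include treatment group (intervention vs control) and the baseline MANSA score to adjust for initial differences". For the random part: "Clinician or healthcare practitioners clusters will be modelled as a random effect to account for intra-cluster correlation". The model equation and the lay restatement below it repeat clinician as the clustering unit.

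The design is set out elsewhere in the protocol:

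- Section 12.7 randomises individuals 1:1 within health centre: "Site-stratified blocked randomisation, with a variable block size ranging from two to four, will be performed on a rolling basis".
- Sections 6, 10.1 and 13.2 say that DD+ is delivered by staff contracted for the trial. Controls continue routine care and receive phone calls.
- Section 16 separates the trial clinician from usual care: "Neither the trial clinician nor the researcher in charge of the follow-up call will be part of the patient care team".
- Section 15.4 lists the imputation covariates as "including study clinician age, sex, clinician, and baseline MANSA score", plus treatment group. Site is not named.
- Section 15.11.7 ties the cost model's cluster to the deliverers: "random effect in the model for healthcare practitioners who delivered DIALOG". It names site fixed effects there, but only if participant characteristics differ between arms.
- Table 7 lists a clinician ID without saying what it holds for a control.

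**The concern.** A provider who delivers DD+ can induce correlation only among the participants they treat, and these are all in the intervention arm. A plain clinician random intercept needs a cluster label for every row, and for controls the protocol supplies none. Different analysts could fill the gap differently and reach different confidence intervals from the same data. The imputation model has the same gap: for a control the DD+ provider does not exist, so it is not a value missing at random that could sensibly be imputed.

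Site is a separate matter. Stratified randomisation balances the arms within site, which removes between-site variation from the true variability of the treatment difference. A model without site leaves that variation in its error terms, so the reported SE is larger than it should be.

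At stake is the standard error of the primary test. The treatment estimate itself hardly changes between codings, provided that the controls stay in the model.

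**Working it through.** **Inputs from the protocol.** SD 0.9, correlation 0.4, difference 0.4, two-sided 5%, 90% power, 20% attrition (15.2); 1:1 allocation stratified by site (12.7); 15 centres (15.11.4).

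**Assumptions.** The protocol gives no ICC and no total number of DD+ providers. Eight providers is an assumption, prompted by section 13.3.3 (up to two invited to interview in each of four regions). Four and 15 are taken as the range. Sites are of equal size.

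**The plan's own figure.** The residual variance after baseline adjustment is 0.81 × (1 − 0.16) = 0.6804.

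- n = 2 × 0.6804 × (1.960 + 1.282)² / 0.16 = 89.4, so 90 per group.
- 90 / 0.8 = 112.5, so 113 per group and 226 in total.
- SE at 90 per group = √(2 × 0.6804 / 90) = 0.123, and power is 90.2%.

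The stated figure is reproduced. It contains no clustering term.

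**Clustering in the DD+ arm only, closed form.** With 8 providers, m = 90/8 = 11.25. At provider ICC 0.05 the DD+ arm's variance is multiplied by 1 + 10.25 × 0.05 = 1.513. Then SE = √(0.6804/90 × 2.513) = 0.138 and power is 82.7%. For ICC 0.01 to 0.10, power is 88.7% to 75.3% with 8 providers, 87.1% to 61.7% with 4, and 89.5% to 82.9% with 15. A correctly coded model must therefore report an SE of about 0.138 at ICC 0.05 with 8 providers.

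**All controls in one cluster, closed form.** The provider variance is 0.05 × 0.6804 = 0.034 and the remainder is 0.646. The model then believes SE = √(0.034 × (1 + 1/8) + 0.646 × 2/90) = 0.229, against the correct 0.138.

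**Simulation.** REML, 1,500 runs per setting, 90 per arm, 15 sites, 8 providers, Wald z test, site ICC 0 to 0.10 and provider ICC 0 to 0.05. The figures are mean model SE divided by empirical SD.

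| Coding of controls | No site variation | Site ICC 0.05 to 0.10 |
|---|---|---|
| Clinician missing | controls dropped, effect not estimable | same |
| One shared cluster | 1.28 to 1.77 over all settings | |
| Grouped by health centre | 0.97 to 1.05 | 1.09 to 1.27 |
| Each control a singleton | 0.98 to 1.04 | 1.05 to 1.15 |
| Zero for controls, no site term | 0.97 to 1.04 | 1.04 to 1.14 |
| Zero for controls, site fixed | 0.98 to 1.02 (provider ICC 0.05) | 1.02 to 1.07 |

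With one shared cluster, type I error is 1.8% to 2.7% and power 45% to 72%. If clinician is ignored altogether at provider ICC 0.05, the ratio is 0.86 to 0.94 and type I error 7.5% to 8.0%. The Monte Carlo standard error is about 0.6 percentage points for a 5% rejection rate, √(0.05 × 0.95 / 1500).

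**What site adds once controls are coded zero.** Power without and with site:

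- site ICC 0.05, provider ICC 0: 87.1% and 88.1%
- site ICC 0.05, provider ICC 0.05: 81.4% and 82.5%
- site ICC 0.10, provider ICC 0.02: 84.5% and 87.5%

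Even with site included the SE is 2% to 7% too large in these settings, so adding site removes part of the excess and not all of it.

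**The case against.** The strongest reply is that the model is under-specified but not wrong. Section 15.7 writes the random part with a general design matrix. Rows of zeros for controls satisfy that equation and give exactly the partially nested model one would want. Singleton clusters do nearly as well. This stands. A reader might infer that the model cannot be fitted without a wrong standard error, and the documents do not support that. Nor do they support presenting power of 45% to 72% as the expected result: it belongs to the single-cluster coding, which no section prescribes.

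It can also be said that controls do have clinicians. Section 15.7 speaks of clinicians or healthcare practitioners, Table 7 does not restrict clinician ID to one arm, and section 15.6 summarises clinician variables in both groups. So the label is ambiguous for controls, not necessarily absent. This does not settle the coding. No section links each control to one practitioner, a single variance would mix DD+ providers with routine-care staff, and section 15.11.7 defines the cluster as those who delivered the intervention.

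On site, sections 15.7 and 16 mention relevant covariates without listing them, so an analysis plan could add site. Omitting it is also conservative and does not inflate false positives. Both points are fair and limit the weight of this half. Site is nevertheless the stratification factor, and naming it is almost free.

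**Conclusion.** The point holds as one of specification. The clinician random effect has no defined value for controls, and site is not named in the primary or imputation model, so the primary SE and p-value depend on a choice that the protocol does not make.

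The possible consequences run from negligible (singleton or zero coding, little site variation), through 28% to 77% too large (one shared control cluster), to not estimable (missing code). Without a site term, the SE is 4% to 15% too large at a site ICC of 0.05 to 0.10, even with singleton or zero coding. Naming site then gains about 1 to 3 points of power in the settings run. All these sizes rest on assumed ICCs, eight providers and equal sites.

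The remaining shortfall from 90% power under correct coding comes from clustering that the sample size does not include. That is a separate matter, which this change does not cure.

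**What to change.** - **15.7:** state the model as 6-month MANSA = treatment + baseline MANSA + site, with a random effect for DD+ provider in the intervention arm only, set to zero for controls.
- **15.4:** add site and impute separately by arm, using provider only within the DD+ arm. No provider is then imputed for a control. Simply dropping clinician from the imputation would not do, because the analysis model would still contain a provider effect that the imputation ignored.
- **15.9:** use the same provider and site terms, and add a participant-level term for the repeated 6- and 12-month measures.
- **15.11.7:** state that the provider effect is zero for controls, and include site as a stratification factor whatever the baseline balance.

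Arm-specific residual variance and the degrees-of-freedom method can be left to the statistical analysis plan.

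The cost is wording, settled before unblinding, and about 14 degrees of freedom (15 sites less one) out of roughly 180 analysed participants if site is a fixed effect. Health centre ID is already collected. Imputing by arm leaves about 113/15 = 7.5 randomised participants per site and arm if sites are equal, so the plan should say how very small sites are handled.
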